#### Appendix D Grading Scale for Adverse Events Relating to Laboratory Abnormalities *Continued*

Adverse Event	Mild	Mild Moderate		
	U	rine		
Proteinuria				
Adults	1+ proteinuria; urinary protein <1.0 g/24 hrs	2+ proteinuria; urinary protein 1.0 - 3.4 g/24 hrs;	Urinary protein ≥3.5 g/24 hrs;	
Children	-	Urine P/C (Protein/Creatinine) ratio 0.5 - 1.9	Urine P/C >1.9	
Hematuria	Asymptomatic; clinical or diagnostic observations only; intervention not indicated	Symptomatic; urinary catheter or bladder irrigation indicated	Gross hematuria; transfusion, IV medications or hospitalization indicated; elective endoscopic, radiologic or operative intervention indicated	

†Grading for this parameter is derived from the Toxicity Grading Scale for Healthy Adult and Adolescent Volunteers Enrolled in Preventive Vaccine Clinical Trials, Sept 2007

\*Grading for this parameter is derived from the Division of AIDS (DAIDS) Table for Grading the Severity of Adult and Pediatric Adverse Events Version 2.0, Nov 2014

‡Modified for consistency with the ADA and Endocrine Society Guidelines (Seaquist ER, Anderson J, Childs B, et al. Hypoglycemia and Diabetes: A Report of a Workgroup of the American Diabetes Association and The Endocrine Society. Diabetes Care 2013;36:1384-95) Appendix E Mixed Meal Test

#### **Appendix E Mixed Meal Test**

At Qualification, 3 months and end of study, subjects enrolled will undergo a meal tolerance test (MTT) as follows: subjects will consume a standardized meal the evening before the test (750 kcal; 20% of energy from protein, 30% from fat, and 50% from carbohydrate) and refrain from consuming alcohol for 72 h.

A cannula will be inserted into a forearm vein, and an overnight fasting (minimum 10 hours) venous blood sample will be taken between 8:00 AM and 10:00 AM for measurement of plasma glucose, FFA, C-peptide and insulin concentrations and serum ghrelin, GIP, GLP-1, and PYY. Incretin hormones will be measured using a multiplex assay (EMD Millipore, Billerica, MA). The tubes for the incretin hormones will contain Pefabloc SC (Sigma-Aldrich, St. Louis, MO) and DPP-IV inhibitor (EMD Millipore, Billerica, MA) to inhibit DPP-IV and other proteases. The change in ratings from Baseline will be quantified.

Subjects will then consume a liquid load of Optifast (Optifast; Novartis, Minneapolis, MN; 474 ml, 320 kcal, 50% carbohydrate, 35% protein, 15% fat) within a 15-min period. Additional blood samples will be taken at 10, 20, 30, 60, 90, 120, 150, 180, 240 and 300 min after meal consumption. VAS will be completed at 180 minutes and 300 min. To calculate the insulin sensitivity index (S1), the oral minimal model for glucose will be used; and to calculate the hepatic insulin extraction, oral minimal model for insulin and c-peptide will be used [Cobelli et al, 2007]. Subjects will complete a validated visual analogue scale (VAS) questionnaire to assess subjective hunger at 0, 180 and 300 minutes [Luscombe-Marsh et al, 2005; Moran et al, 2005].

Appendix F Laboratory Tests to Be Performed in the Event of a Platelet Count < 100,000/mm^3

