# 3.4.1 Screening/Qualification

Subject eligibility for the study will be determined within 42 days/6 weeks prior to study entry. Potential subjects will report to the Study Center for screening assessments at specified intervals within the 6-week screening period as detailed in the Schedule of Procedures in Appendix A. As part of the screening period, subjects will have a 4-week diet stabilization/run-in period followed by a up to 2-week qualification period. Subjects on stable diet known to the investigator and followed at the site may go from Screening to qualification without a 4-week diet run-in. At the qualification visit TGs will be measured. A baseline DEXA scan and MRI will be obtained to assess liver fat content once all other eligibility has been confirmed. MRI results must be available prior to registration and administration of the first dose of study drug.

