# \*Note: A female condom and a male condom should not be used together as friction between the two can result in either or both products failing.

# 6.3.2 Other Requirements

All subjects will be required to fast for at least 10 hours before visits requiring fasted blood sampling.

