#### **10. STATISTICAL CONSIDERATIONS**

#### 10.1 Study Endpoints, Subsets, and Covariates

#### 10.1.1 Primary Endpoint

• The effect of ISIS 703802 on the percent change from Baseline in fasting triglyceride levels (TG) at week 27

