# **10.4 Definition of Baseline**

For fasting lipid measurements, the Baseline is defined as the average of Day 1 pre-dose assessment and the last measurement prior to Day 1.

For other measurements, Baseline will be the last non-missing assessment prior to the first dose of Study Drug.

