# Appendix ASchedule of Procedures Continued

	Scree	ning		Treatment Period					Follow-up Period				
	Run-in #	Qual †											
Study Week	-6 to -1	-1 to 0	1	5	9	13	17	21	25	27/ET	4*	8*	13*
Study Day	-42 to -1	-7 to -1	1	29	57	85	113	141	169	183		from the ment pe	e end of riod o
Visit and Testing Window +/- Days	0	0	0	2	2	2	3	3	3	0	3	3	3
Hematology	Х			-		EVERY 14 D	DAYS (+/- 2	days) f			X h	X h	X h
Coagulation	Х		Х							Х			
Hepatitis B, C, HIV	Х												
Thyroid Panel	Х												
Inflammatory			Х			Х				Х			Х
Liver Biomarkers			Х			Х				Х			Х
Plasma PK - ISIS 703802 I			X 	X 	X 	X 	X 	X 	X 	Х	Х	Х	Х
Anti-ISIS 703802 Antibodies			Х	Х	Х	Х		Х		Х		Х	Х
FSH (women only, if applicable) j, m	Х												
Serum Pregnancy Test m	Х		Х	Х	Х	Х	Х	Х	Х	Х	Х	Х	
Archived Serum & Plasma Samples $_{j,n}$			х		х		х			Х			х
PD Panel j	Х	Х	Х	Х	Х	Х	Х	Х	Х	Х	Х	Х	Х
Extended Lipid Panel j	Х	Х	Х	Х	Х	Х	Х	Х	Х	Х	Х	Х	Х
HbA1C j	Х		Х			Х				Х			Х
Quality of Life Assessment		Х				Х				Х			
Widespread Pain Diary		Х			TO E	BE DONE AT	OUTPATIE	ENT VISITS			Х	Х	Х
Study Drug: SC Injection			WEEK	WEEKLY SUBCUTANEOUS ADMINISTRATION OF STUDY DRUG (Week 1 through Week 26/Day 176)									
Adverse Events		TO BE COLLECTED FROM TIME OF INFORMED CONSENT TO END OF FOLLOW-UP PERIOD											
Concomitant Medication			TO BE (	COLLECTE	D FROM T	IME OF INFO	ORMED CC	NSENT TO	END OF FOLL	OW-UP PE	RIOD		

1010 / 00 002 00		
Protocol		16 February 2018
Appendix A	Schedule of Procedures Continued	

CONFIDENTIAL

Amendment 1

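### The Week 27 triglyceride draw follows mixed-meal-test preparation, but the Day 1 half of its baseline requires only a fast, so the uncontrolled primary endpoint may be biased by an amount and in a direction the documents do not give

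*Combined protocol and SAP*

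**What the plan says.** All references are to Protocol Amendment 1.

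- **Endpoint.** Section 10.1.1 makes the primary endpoint the "percent change from Baseline in fasting triglyceride levels (TG) at week 27".
- **Baseline.** For fasting lipids, Section 10.4 uses "the average of Day 1 pre-dose assessment and the last measurement prior to Day 1". The prior measurement is normally the Qualification value, since Section 3.4.1 states: "At the qualification visit TGs will be measured".
- **Meal test timing.** Appendix E: "At Qualification, 3 months and end of study, subjects enrolled will undergo a meal tolerance test". Appendix A marks the test at Qualification, Week 13 and Week 27, with no mark on Day 1.
- **Meal test preparation.** Appendix E prescribes a standard evening meal (750 kcal; 20% protein, 30% fat, 50% carbohydrate), a fast of at least 10 hours, and that subjects "refrain from consuming alcohol for 72 h".
- **Lipid draw preparation.** Appendix A marks the "Extended Lipid Panel" at every visit. Footnote j asks for an overnight fast of at least 10 hours, ideally no longer than 12. Section 6.3.2 adds only: "All subjects will be required to fast for at least 10 hours before visits requiring fasted blood sampling". Neither sets an alcohol or evening-meal rule.
- **Windows.** Week 27 is Day 183 with a 0-day window. The Qualification column spans Day −7 to Day −1.

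**The concern.** With a 0-day window, the Week 27 lipid panel and meal test fall on the same day, and a fasting TG has to come before the liquid meal. So the endpoint draw follows three days without alcohol and a fixed evening meal. On Day 1 a subject may have drunk and eaten as usual up to the start of the fast. The two sides of the primary contrast are therefore not collected under the same conditions.

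A randomised control arm would cancel a systematic difference between visits. This trial has one arm and about 3 subjects (up to 6), so nothing cancels it and any preparation effect is counted as drug effect. The reading also has a use: Section 3.1 lets enrolment grow partly on efficacy observations. The same baseline rule covers the other fasting lipids, so secondary lipid endpoints share the mismatch.

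**Working it through.** The protocol states no power, alpha or SD (Section 10.2 gives no statistical rationale for the sample size), so there is no planned figure to reproduce. The check is bias algebra.

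**Inputs**

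- *d*: fractional lowering of fasting TG by meal-test preparation. It is not in the documents. I take 5%, 10% and 20% as assumptions, with 0 and −10% (preparation raises TG) for contrast.
- *e*: true drug reduction. I take 0, and 63% as predicted in Section 2.4.
- *T*: a subject's TG under fast-only conditions before treatment.

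**Case A: Qualification TG drawn on the meal-test morning**

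Baseline = [T(1−d) + T]/2 = T(1−d/2)

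Week 27 = T(1−d)(1−e)

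Observed change = (1−d)(1−e)/(1−d/2) − 1

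Bias = observed change + e = −(1−e)(d/2)/(1−d/2)

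Example: d = 0.10 and e = 0 gives −0.05/0.95 = −5.3 points. With e = 0.63 it is 0.37 × (−5.26) = −1.9 points.

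**Case B: Qualification TG drawn on another, fast-only day**

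Baseline = T, so bias = −(1−e)d.

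| Assumed d | A, e = 0 | A, e = 63% | B, e = 0 | B, e = 63% |
|---|---|---|---|---|
| −10% | +4.8 | +1.8 | +10.0 | +3.7 |
| 0 | 0 | 0 | 0 | 0 |
| 5% | −2.6 | −0.9 | −5.0 | −1.9 |
| 10% | −5.3 | −1.9 | −10.0 | −3.7 |
| 20% | −11.1 | −4.1 | −20.0 | −7.4 |

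Entries are percentage points of percent change. In Case A at e = 63%, a 5-point bias needs d of about 24%, and a 10-point bias about 43%.

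**After the fix.** With Day 1 also prepared, baseline = T(1−d) and the observed change is −e exactly, whatever d is.

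**Week 25 against Day 1.** Neither visit has a meal test, so the ratio is T(1−e)/T and preparation drops out. Time since dosing also matches. On the weekly schedule, doses 24 and 26 fall on Day 1 + 23×7 = 162 and Day 1 + 25×7 = 176, so the Day 169 pre-dose draw and the Day 183 draw each come 7 days after a dose. The cost is one baseline draw instead of two. With independent draws of equal within-subject CV, the standard error rises by √(2/1.5) = 1.155, about 15%. With n = 3, no drug effect and an assumed CV of 20%, it goes from √(1.5 × 0.04/3) = 14.1 to √(2 × 0.04/3) = 16.3 points.

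**The case against.** A reader might infer that the plan builds a spurious fall into the primary endpoint. The documents do not support that. Nothing in them says that 72 hours without alcohol, or this particular meal, lowers fasting TG, and nothing records subjects' drinking or usual evening meal. For a non-drinker whose usual meal acts like the standard one the bias is zero. If the standard meal raises fasting TG relative to the usual one, the bias runs against the drug.

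Existing controls also narrow the gap. Every lipid draw is fasting, recent alcohol abuse is excluded (exclusion 10), subjects follow a moderate diet (inclusion 7) with a run-in unless already stable, and the Qualification half of the baseline belongs to a meal-test visit. At the predicted 63% fall, an assumed 5 to 20% effect moves the result by only 0.9 to 4.1 points. The analysis is descriptive, with no success threshold for such a shift to cross.

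Most of this stands, and it limits the point to a possible bias, probably modest if the drug works as predicted. It does not remove the mismatch. The diet criterion does not fix the meal before a draw, the alcohol exclusion does not reach ordinary drinking, and the protocol does not say that the Qualification TG and meal test share a morning.

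**Conclusion.** The difference in preparation is real in the current text. Its effect on the primary endpoint is possible but unquantified. If preparation is assumed to lower TG by 5 to 20%, and the Qualification TG is drawn on the meal-test morning, the bias is −2.6 to −11.1 points with no drug effect and −0.9 to −4.1 points at a 63% reduction. It roughly doubles if the Qualification draw is on another day, vanishes if preparation has no effect, and changes sign if preparation raises TG. These figures also assume that Day 1 is in fact unprepared; a subject may happen to have prepared, but nothing requires it.

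Over this range the mismatch could not by itself produce a fall of around 60%. It would matter if the drug effect were small. The correction is worth making because it is cheap and works whatever the sign or size.

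**What to change.** **Going forward**

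- In Appendix A footnote j and Section 6.3.2, require the meal-test alcohol rule and standard evening meal, as well as the fast, before the Day 1 lipid draw.
- State that Qualification lipids are drawn fasting on the meal-test morning, before the liquid meal.
- Reconcile Section 6.2.5 and the synopsis (meal test at baseline, 8-hour fast) with Appendix E (Qualification, 10-hour fast), so that the timing has one reading.

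The cost is one more standard meal and a slight burden on subjects.

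**Subjects already enrolled**

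- List Qualification and Day 1 TG side by side for each subject. This is a rough check: at an assumed 20% CV the mean difference in 3 subjects has a standard error of about 16.3 points.
- Show Week 25 against Day 1 as a preparation-matched sensitivity comparison. It needs no new data and costs the roughly 15% loss of precision shown above.

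A Qualification-only baseline is a tempting alternative but should not be used. Inclusion 5 selects subjects on their Qualification TG, so using it alone increases regression to the mean and can itself create an apparent fall. The protocol does not place that draw on the meal-test morning, and a single draw loses the same precision.

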# Appendix F Laboratory Tests to Be Performed in the Event of a Platelet Count < 100,000/mm3\*

\*Labs only need to be performed once. Labs may be collected over multiple visits, if blood requirements are a concern, as per Investigator discretion

Note: The following labs may change as additional data is assessed, and sites will be updated regarding any changes.

To Be Performed at Local Lab
Peripheral smear (should be performed locally, fixed and sent to central lab for review)
Fibrinogen split products or D-dimer on fresh blood
To Be Performed at Central Lab
Citrated sample for platelets
Coagulation panel (PT/INR, aPTT)
CBC with reticulocytes
Folate (folic acid)
Vitamin B12
Fibrinogen
von Willebrand factor
Total globulins, total IgA, IgG and IgM
Complement: total C3, total C4, Bb, C5a
hsCRP
Helicobacter pylori (breath test)
Serology for:
HBV, HCV, HIV (if not done recently for screening)
Rubella
CMV
EBV
Parvo B19
Auto-antibody screen:
Antiphospholipid
Rheumatoid factor
Anti-dsDNA
Anti-thyroid
To Be Performed at Specialty Lab(s)
Antiplatelet antibodies and Anti-PF4 assay
Anti-ASO antibody

# ISIS 703802-CS05: Administrative Clarification Letter 1 to Protocol Amendment 1

11 September 2018

# RE: Protocol ISIS 703802-CS5: An open-label Phase 2 Study of ISIS 703802 (AKCEA-ANGPTL3-LRx) Administered Subcutaneously to Subjects with Familial Partial Lipodystrophy, Protocol Amendment 1 dated 16 February 2018

Dear Investigators:

The following administrative clarifications are being issued for Protocol ISIS 703802-CS5 Amendment 1.

#### Administrative Clarification 1 – Section 6.2.1 Physical Exams and Vital Signs

#### Current Text:

Physical exams and vital signs will be performed as indicated in the Schedule of Procedures (Appendix A). Vital signs should include weight, blood pressure (BP), pulse rate, respiratory rate and body temperature. BP and pulse rate will be recorded after the subject has been in a sitting position for at least 5 minutes. BP should always be measured on the same arm (preferentially on the left arm). Height will be measured at Screening.

#### Clarification: (new text indicated in **bold**)

Physical exams, vital signs, and skin fold measurements will be performed as indicated in the Schedule of Procedures (Appendix A). Vital signs should include weight, blood pressure (BP), pulse rate, respiratory rate and body temperature. BP and pulse rate will be recorded after the subject has been in a sitting position for at least 5 minutes. BP should always be measured on the same arm (preferentially on the left arm). Height will be measured at Screening. Skinfold measurements will be recorded as per the Schedule of Procedures (Appendix A) starting at Day 1 Pre-dose. Skinfold measurements will be collected from each subject's right mid anterior thigh and right tricep.

#### Rationale:

The secondary endpoints include "Changes from Baseline in body fat distribution for various areas in the body as measured by skinfold thickness and DEXA." The purpose of this clarification it to provide omitted details regarding the collection of skinfold measurements that were missing from Section 6: Study Procedures. This measurement will occur at every visit in which a physical exam (full or abbreviated) occurs.

#### Administrative Clarification 2 – Appendix A Schedule of Procedures – Skinfold Measurements

#### Current Text:

None.

#### Clarification: (new text indicated in **bold**)

[figure not shown]
Skinfold Measurements: Performed at Study Day 1 (Pre-dose) and at Weeks 5, 13 and 27/ET, and during the Follow Up Period at Weeks 4 and 13.

#### Rationale:

The secondary endpoints include "Changes from Baseline in body fat distribution for various areas in the body as measured by skinfold thickness and DEXA." It has come to our attention that the details of the collection and specific timepoints of collecting skinfold measurements were missing from Appendix A: Schedule of Procedures. Skin fold measurements will occur as part of the physical exam and therefore, this measurement will occur at every visit in which a physical exam (full or abbreviated) occurs.

#### **Summary**

This Administrative Clarification Letter serves to align the planned secondary endpoints with Section 6: Study Procedures and Appendix A: Schedule of Procedures. It is noted that no safety assessments or procedures have been added or removed. This clarification does not affect the rights, safety, or well-being of study participants.

Akcea Therapeutics, Inc.

cc: ISIS 703802-CS5 Study Coordinators, ISIS 703802-CS5 TMF

# ISIS 703802-CS5: Administrative Clarification Letter 2 to Protocol Amendment 1

#### 02 October 2018

# RE: Protocol ISIS 703802-CS5: An open-label Phase 2 Study of ISIS 703802 (AKCEA-ANGPTL3-LRx) Administered Subcutaneously to Subjects with Familial Partial Lipodystrophy, Protocol Amendment 1 dated 16 February 2018

#### Dear Investigators:

The following administrative clarifications are being issued for Protocol ISIS 703802-CS5 Amendment 1.

#### Administrative Clarification 1 – Appendix A Schedule of Procedures – Footnote H

#### Current Text:

During follow-up period, hematology sampling for platelet values are taken every 14 days (+/- 2 days) for 6 weeks after last dose of Study Drug, then at Week 8 and Week 13 Follow-up visits.

#### Clarification: (new text indicated in **bold**)

During the treatment period, hematology sampling for platelet values are taken every 14 days (+/- 2 days) from first dose through 6 weeks post treatment period, then at Week 8, and Week 13 Follow-up visits.

#### Rationale:

Clarification to footnote H of the Schedule of Procedures in order to align with the timing for hematology sampling following the treatment period.

#### **Summary**

This Administrative Clarification Letter serves to align the timing for hematology sampling as outlined in the Schedule of Events Table in Appendix A. It is noted that no safety assessments or procedures have been added or removed. This clarification does not affect the rights, safety, or well-being of study participants.

#### 02 July 2019

## RE: Protocol ISIS 703802-CS5: An open-label Phase 2 Study of ISIS 703802 (AKCEA-ANGPTL3-LRx) Administered Subcutaneously to Subjects with Familial Partial Lipodystrophy

Dear [name]:

The following administrative clarification is being issued for Protocol ISIS 703802-CS5 Protocol Amendment 1.

#### Administrative Clarification:

Appendix B: List of Laboratory Analytes

Current Text: Extended Lipid Panel: Ceramides, Sphingolipids, Diacyglycerol

Clarification Text: Remove: Ceramides, Sphingolipids, Diacyglycerol

#### Rationale:

Akcea Therapeutics Inc. uses protocol template language as part of its process on developing study protocols. When writing the ISIS 703802-CS5 Protocol, the analytes Ceramides, Sphingolipids, and Diacyglycerol were included in the text of Appendix B as part of template language and were unintentionally left in the List of Laboratory Analytes at protocol finalization. There was never an intention to run those analytes in this study or within this patient population.

#### Summary

This Administrative Clarification Letter serves to clarify the intended analytes to be studies as listed in the Appendix B List of Laboratory Analytes. Safety assessments, inclusion, or exclusion were not added or removed. This clarification does not affect the rights, safety, or well-being of study participants.

Akcea Therapeutics, Inc.
